17.3. Safety

17.3.1. Safety Endpoints

The safety endpoint will be a descriptive analysis of adverse events (AEs) for both study arms, classified and tabulated by seriousness, relationship to the device, and severity.

17.3.2. Safety Analysis

Frequency charts of adverse events occurring at any time during the study will be produced. The proportion of subjects having one or more adverse events between randomization and the Day 28 will be calculated and compared using a comparison of proportions test. The proportion of subjects reporting on or more adverse events at the Day 56 will tabulated. Similar analyses will be done for SAEs and device-related SAEs. Safety analysis will include all subjects who were treated. A Statistical Analysis Plan (SAP) will be developed prior to breaking the blind, which may include additional plans for safety analysis.

17.4. Blinding Analysis

A Statistical Analysis Plan (SAP) will be finalized prior to breaking the blind, which will include a plan for blinding analysis. The extent to which subjects remained blinded at the end of Phase 1 will be assessed by calculating a blinding index based on data from the Blinding Assessment following Phase 1, in which subjects will be asked what treatment they believe they received. Further, participants who guess that they received "Treatment" or "Sham" (as opposed to "Don't Know") will be asked for the primary reason for their guess and these results will be analyzed.

17.5. Exploratory Analysis

Additional statistical analysis that is exploratory in nature may be performed.

18. Remote procedures

During and after the COVID-19 pandemic, replacing some in-person visits with remote interactions may be necessary, for example to reduce risk to subjects and/or to comply with local, state, or federal regulations. In such cases, the study records will indicate which in-person visits were replaced with remote interactions. The allowable study duration may be expanded as needed to allow delay intervals for mailing and receiving programmed devices.

In such cases, one of more of the following approaches may be taken:

- Remote calibration and training. Remote calibration and training, where possible, will be coordinated by mailing a calibration/training device to the subject, conducting calibration and training via a video call using the calibration/training device, and then mailing programmed devices to the subject using the settings determined during the calibration. Alternatively, the same devices used in the study may be used for calibration/training.
- 2. Remote follow-up visits. Remote follow-up visits, where possible, will be completed via call or video call, during which the required study assessments will be administered.
- 3. Devices may be returned using a pre-paid mailing label, as needed.
- 4. Remote consent. Remote consent procedures will follow the recommendations set forth in the "FDA Guidance on Conduct of Clinical Trials of Medical Products during COVID-19 Public Health Emergency" [14]. For example, or more of the following procedures listed in the guidance will be used to confirm consent:
 - a. eConsent via a compliant digital platform;
 - b. confirmation of consent by an impartial witness via three-way call or video conference;
 - c. remote explanation of consent followed by in-person signature of informed consent document (to minimize duration of in-person interaction).

19. References

- Allen, R.P. et al. Restless legs syndrome: diagnostic criteria, special considerations, and epidemiology. A report from the restless legs syndrome diagnosis and epidemiology workshop at the National Institutes of Health. Sleep Med. (2003). doi: 10.1016/s1389-9457(03)00010-8
- 2. 2012 Revised IRLSSG Diagnostic Criteria for RLS. Available at: http://irlssg.org/diagnostic-criteria

### **List of Abbreviations**

Abbreviation	Definition
AE	Adverse Event
AO	Anticipated Observation
CGI-I	Clinical Global Impressions – Improvement
FDA	Food and Drug Administration
FCS	Fully Conditional Specification
IRLS	International Restless Legs Syndrome Study Group Rating Scale
IRLSS	International Restless Legs Syndrome Society
ITT	Intent-to-Treat
MAR	Missing at Random
MedDRA	Medical dictionary for Regulatory Activities
MI	Multiple Imputation
MOS	Medical Outcomes Study
NPNS	Non-invasive peripheral nerve stimulation
PGI-I	Patient Global Impressions – Improvement
PP	Per Protocol
PT	Preferred Term
RLS	Restless Legs Syndrome
SAE	Serious Adverse Event
SOC	System Organ Class

### 1.0 INTRODUCTION

This document details the analysis plan for the study entitled "A Multi-Center, Randomized, Double-Blind, Sham-Controlled Study to Evaluate the NTX100 Neuromodulation System for Patients with Medication-Refractory Primary Restless Legs Syndrome (RLS) – The RESTFUL study". It describes the proposed efficacy and safety analyses, including planned summary tables, by-subject data listings, and figures.

A clinical need has been identified of improved treatment for those suffering with primary idiopathic restless legs syndrome (RLS). Patients with RLS have a strong urge with sensations of tingling/pain, usually in their legs, and often present with a primary complaint of not being able to fall asleep regularly. This leads to significant quality of life degradation, depression, daytime sleepiness, lack of productivity, and a host of downstream effects associated with lack of quality sleep.

Restless legs syndrome is a sensorimotor disorder that is characterized by a distressing urge to move the legs and, in some cases, other parts of the body such as arms. The diagnosis is made by a response to five hallmark identifying criteria instituted by the International Restless Legs Syndrome Society (IRLSS), as quoted below:

- "1. An urge to move the legs usually but not always accompanied by or felt to be caused by uncomfortable and unpleasant sensations in the legs.
- 2. The urge to move the legs and any accompanying unpleasant sensations begin or worsen during periods of rest or inactivity such as lying down or sitting.
- 3. The urge to move the legs and any accompanying unpleasant sensations are partially or totally relieved by movement, such as walking or stretching, at least as long as the activity continues.
- 4. The urge to move the legs and any accompanying unpleasant sensations during rest or inactivity only occur or are worse in the evening or night than during the day.
- 5. The occurrence of the above features are not solely accounted for as symptoms primary to another medical or a behavioral condition (e.g., myalgia, venous stasis, leg edema, arthritis, leg cramps, positional discomfort, habitual foot tapping)."

Diagnostically, RLS is considered either primary, often occurring within families, or secondary, developing in association with other conditions (such as iron deficiency anemia, pregnancy, or end-stage renal disease).

In the United States, RLS is believed to affect more than 10 million adults and an estimated 1.5 million children and adolescents. About one-third of those with RLS symptoms are bothered sufficiently enough to seek medical attention. Epidemiologic studies also show that women are at least 50% more susceptible to RLS than men and RLS is more common in older adults, although it can occur in some as early as the pre-school years.

The current standard of care involves initial prescription of dopaminergic medications – such as Requip, Mirapex, and Neupro – that initially provide symptomatic relief but often become

ineffective over continued usage. Tolerance to these medications is rapid and well-documented; approximately 10% of patients per year become refractory to these medications, and fewer than 20% patients have sustained benefits lasting 10 years or longer. It is also now understood that dopaminergic medications cause what is known as "augmentation", or paradoxical progressive worsening of RLS symptoms that is much faster than the natural progression of the condition. Due to augmentation, patients on dopaminergic medications require increasingly higher doses. Maximal dosage is limited by an increasing risk of side-effects at higher doses, which include compulsive behaviors including substance abuse, hypersexuality, and gambling. As a result of these downsides of dopaminergic agents, a minority of clinicians are starting to prescribe gabapentinioids (e.g., Horizant) as an alternative first-line of treatment; these medications do not typically lead to augmentation but confer risks such as respiratory depression, dizziness, and somnolence during the day.

For the large subpopulation of patients who become refractory to dopaminergic medications – typically due to augmentation – there are no FDA approved treatment options and no safe treatment options. As a result of tolerance, augmentation, and dosage limitations, RLS patients often continue to suffer from moderate-severe RLS symptoms while continuing to be reliant on high doses of dopaminergic medications to provide a small degree of relief. To address the massive unmet need, the leading clinicians involved with RLS advocate prescribing off-label opioids. The leading options, oxycodone and methadone, have well documented risks, which include addiction, dependence, overdose, and occasionally death. This situation is especially concerning because primary RLS typically starts in middle age or earlier and persists throughout life, thus patients may end up reliant on opioids for the final decades of their lives.

The investigational device – the NTX100 Neuromodulation System – is a non-invasive nerve peripheral stimulation (NPNS) device developed by Noctrix Health, Inc. (Sponsor) and is designed to bilaterally stimulate the common peroneal nerve. Stimulation electrodes are positioned superficially and bilaterally on the lower legs over the head of the fibula bone, a position where the peroneal nerve is closest to the skin. This nerve target innervates regions of the lower extremities commonly associated with RLS symptoms.

This study evaluates the effects of NPNS on the symptoms of RLS during in-home subject-administered stimulation. This approach is useful for evaluating safety, usability, tolerability, and preliminary efficacy in a realistic environment, thus identifying any and all barriers to effective and tolerable use.

### 2.0 STUDY OBJECTIVE

The study objective is to provide comparative evidence assessing clinically meaningful benefit in the treatment of patients with moderate to severe medication-refractory RLS with the NTX100 Neuromodulation System.

### 3.0 STUDY DESIGN

[figure not shown]
### 3.1 Overview

The study consists of a 4-week prospective, randomized, sham-controlled, double-blinded phase (Phase 1) followed by a 4-week prospective open-label phase (Phase 2) for a total of 8-weeks of follow-up per subject. The design of the trial is illustrated in the flowchart below (Figure 1).

Phase 1 (4 weeks): Subjects who pass screening will be randomly allocated at a 1:1 ratio to receive Active or Sham treatment throughout the 4-week duration of Phase 1. The primary endpoint and key secondary efficacy endpoints #1-5 will compare the final week of Phase 1 to study entry ("Baseline").

Phase 2 (4 weeks): All subjects who complete Phase 1 will be allocated to receive open-label Active treatment throughout the 4-week duration of Phase 2. Key secondary efficacy endpoint #6 will compare the final week of Phase 2 to Baseline among subjects who receive Active treatment during both Phase 1 and Phase 2.

Figure 1: Study Design Flowchart

The schedule of assessments for this study is presented in Table 1.

**Table 1: Schedule of Assessments** 

	EVAL 1	EVAL 2	EVAL 3	EVAL 4	EVAL 5	EVAL 6	EVAL 7	EVAL 8	EVAL 9	EVAL 10	EVAL 11
	Day 0* in-office	Day 3	Day 7	Day 14 in-office	Day 21	Day 28 in-office	Day 31	Day 35	Day 42	Day 49	Day 56 in-office
Informed Consent	X										
Screening	Х										
Subject characterization	Х										
Medical History	Х										
Refractory categorization	Х										
Concomitant Medications	Х			Х		Х			Х		Х
Randomized receipt of	Х										
Treatment or Sham Device											
Begin open-label use of						Х					
Treatment Device											
Daily Questionnaire		Х	Х	Х	Х	Х	Х	Х	Х	Х	Х
follow-up											
Weekly questionnaire and follow-up			Х	Х	Х	Х		Х	Х	Х	Х
CGI-I						Х					Х
PGI-I				Х		Х			Х		Х
IRLS	Х			Х		Х			Х		Х
MOS-Sleep	Х					Х					Х
Custom RLS questionnaire						Х					Х
Blinding Assessment						Х					
Adverse Events		Х	Х	Х	Х	Х	Х	Х	Х	Х	Х

\* If EVAL 1 spans multiple days, Day 0 refers to the final day of EVAL 1.

### 3.2 Method of Assigning Subjects to Treatment

Subjects who meet eligibility criteria will be randomized in a 1:1 ratio for Phase 1 to either:

- NTX100 programmed to ACTIVE mode
- NTX100 programmed to SHAM mode

Randomization assignments will be stratified by study center with randomly chosen block sizes of 4 or 6.

### 3.3 Blinding

Phase 1 will be double-blind. Information about treatment assignment will be concealed from subjects, investigators, and site staff, except as required in cases of safety emergencies. In additional, all sponsor staff interacting directly with the research staff or investigators (e.g., in a monitoring capacity) or subjects (e.g., in a device specialist capacity) will be blinded to the Phase 1 treatment assignment throughout the study (even during Phase 2).

Phase 2 will be open-label. At the beginning of Phase 2, the treatment assignment on each device will be set to Active for all subjects. This will take place without revealing the previous treatment assignment during Phase 1.

Active and sham devices will be physically identical and will provide identical visual feedback during operation. Both active and sham mode will have an initial ramp-up in stimulation intensity lasting approximately 30 seconds and during which sensations are typically noticeable. No subjects with prior experience with NTX100 nor prior experience using any neurostimulation devices to treat RLS symptoms will be enrolled.

The investigator must contact the sponsor if the need to unblind arises. The Investigator should not unblind UNLESS knowledge of the subject's treatment assignment is required for the subject's clinical care and safety. Documentation of breaking the blind should be recorded in the subject's *Narrative eCRF* with the date and time the blind was broken, and the names of the personnel involved.

### 3.4 Determination of Sample Size

Sample size estimates were based on data from use of an earlier prototype of this investigational device in a previously approved protocol (RLS-SNS01). Based on these data and assuming a 1:1 allocation to treatment, statistical power of 85%, and a two-sided alpha of 0.05 (or one-sided alpha of 0.025):

- For CGI-I responder rate at Week 4 of Phase 1, the sample size needed is 42 subjects, assuming statistical analysis with a two-proportion normal approximation test.
- For PGI-I responder rate at Week 4 of Phase 1, the sample size needed is 42 subjects, assuming statistical analysis with a two-proportion normal approximation test.
- For reduction in IRLS score at Week 4 of Phase 1, the sample size is 112 subjects, assuming statistical analysis with a two-sample t-test.
- For CGI-I score at Week 4 of Phase 1 relative to Baseline, the sample size needed is 36 subjects, assuming statistical analysis with a two-sample t-test.

The maximum of these sample sizes is 112 subjects. Previous data with this investigational device are not available for the MOS-I or MOS-II. Based on estimates of a 15% dropout rate, approximately 132 subjects will be enrolled in the study to yield approximately 112 completed subjects.

### 3.5 Changes to the Protocol-Specified Analyses

Reduction in IRLS Question #7 score ("How often do you get RLS symptoms?") from Baseline to Week 8 was added as a key secondary efficacy endpoint for subjects assigned to NTX100 in both phases of the study. A summary of the same reduction from Week 4 to Week 8 was added for subjects switching from Sham to NTX100 after Week 4.

### 4.0 EFFICACY ENDPOINTS

### 4.1 Primary Efficacy Endpoint

The primary efficacy endpoint is the response on the Clinical Global Impressions-Improvement (CGI-I) scale at Week 4 of Phase 1 relative to Baseline (study entry). A "successful" response for the 7-point CGI-I scale will be defined as a response of "Much Improved" or "Very Much Improved".

### 4.2 Key Secondary Efficacy Endpoints

The key secondary efficacy endpoints are as follows:

- 1. PGI-I response (defined as for CGI-I) at Week 4 of Phase 1 relative to baseline.
- 2. Reduction in IRLS score at Week 4 of Phase 1 relative to Baseline.
- 3. Reduction in MOS-II (Medical Outcomes Study Sleep Problems Index I) score at Week 4 of Phase 1 relative to Baseline.
- 4. Reduction in MOS-I (Medical Outcomes Study Sleep Problems Index II) score at Week 4 of Phase 1, relative to Baseline and compared between study arms.
- 5. CGI-I score at Week 4 of Phase 1 relative to Baseline.
- 6. For subjects assigned to NTX100 in both Phases 1 and 2, reduction in IRLS Question #7 score ("How often do you get RLS symptoms?") from Baseline to Week 8.

### 5.0 STATISTICAL CONSIDERATIONS

### 5.1 General Methodology

The statistical analysis of the data obtained from this study will be performed using SAS® version 9.4 or higher.

Data collected in this study will be documented using summary tables, subject data listings, and figures. Continuous variables will be summarized using descriptive statistics, specifically the mean, median, standard deviation, minimum and maximum. Categorical variables will be summarized using frequencies and percentages. For continuous data, the minimum and the maximum will use the same decimal place accuracy as the raw data. The mean, median, and standard deviation will use one more decimal place than the raw data. For categorical data, percentages will be reported to one decimal place. P-values will be reported to 4 decimal places. P-values less than 0.0001 will be displayed as <0.0001 in the tables. All statistical tests for efficacy will be performed at the one-sided 0.025 significance level, and all statistical tests for safety (adverse events) will be performed at the two-sided 0.05 significance level.

Data listings will be sorted by site number and subject ID number.

### **5.2** Adjustments for Covariates

There will be no adjustment for covariates in any efficacy or safety analysis, unless there are missing data for the primary efficacy endpoint and multiple imputation methods are used (see Section 5.3). Only the logistic regression analysis conducted to assess the blinding will include adjustment for covariates. The dependent variable for this analysis will be the participant's guessed treatment, and the explanatory variables will be the participant's actual treatment and the following two PGI-I Day 28 indicator variables as covariates: (1) being at least "minimally improved" and (2) being at least "much improved".

### 5.3 Handling of Dropouts and Missing Data

If there are any missing data for the primary efficacy endpoint, multiple imputation (MI) methods will be used to impute the missing data. Using SAS® PROC MI, the logistic regression method of imputation will be used with treatment group and the following covariates as explanatory variables: IRLS at Days 0 and 14 and PGI-I at Day 14. This method of multiple imputation is appropriate for a binary dependent variable with explanatory variables following a monotone missing pattern and assumes that the data for the dependent variable are missing at random (MAR). If the data do not follow a monotone missing pattern, the fully conditional specification (FCS) method will be used to impute missing data. For each imputed dataset, PROC FREQ of SAS® will be used to obtain the responder rate and the corresponding standard error for each treatment. PROC MIANALYZE of SAS® will be used to combine the results from the imputed datasets to produce an overall estimate of the true responder rate and the corresponding 95% confidence interval for each treatment. The estimated difference in true responder rates and the p-values for the test for superiority of NTX100 to sham control from a normal approximation test will also be presented.

### 5.4 Interim Analyses

No interim analyses are planned.

### 5.5 Multicenter Study

This is a multicenter study. Four to eight clinical sites within the United States will participate in the study.

### **5.6** Multiple Comparisons / Multiplicity

The fixed sequence method of statistical testing will be used for the primary and key secondary efficacy endpoints. In order to control the overall type I error rate, the key secondary efficacy endpoints will be tested in a hierarchical, gatekeeping manner in the order specified in Section 4.2, and only if primary efficacy endpoint success has been achieved. If one key secondary efficacy endpoint does not meet statistical significance in favor of NTX100, formal testing of subsequent key secondary efficacy endpoints will not be conducted.

### 5.7 Examination of Subgroups

No subgroup analyses are planned.

### 6.0 ANALYSIS POPULATIONS

### 6.1 Intent-to-Treat (ITT) Population

The Intent-to-Treat (ITT) Population will include all eligible subjects who pass screening and are randomized into the study.\* The ITT Population Set will be used for the primary analysis of all efficacy endpoints, and subjects will be analyzed based on the treatment to which they are randomized.

### 6.2 Per Protocol (PP) Population

The Per Protocol (PP) population will include all subjects who pass screening, are randomized into the study, undergo the assigned treatment, and have complete and evaluable Day 28 data, except that:

- (i) Subjects will be excluded from the Per Protocol Population if one or more of the following occurs during or before the Phase of the study corresponding to the endpoint:
  - 1. Dropout or removal from the study.
  - 2. Incomplete or missing data for the endpoint.
  - 3. Clinically significant change in dose or schedule of one of the following classes of medication during the study: RLS medications, antidepressants, sleep medications, or sedative antihistamines.
  - 4. New medical information available after randomization indicates an exclusion criterion.
  - 5. Other protocol deviation occurs that is deemed clinically significant by the investigator.
- (ii) Subjects will also be excluded from the Per Protocol Population if one or more of the following occurs during the Phase of the study corresponding to the endpoint:
  - 6. Device usage on fewer than two-thirds of the nights with RLS symptoms as reported by the subject on the Daily Questionnaire assessments.
  - 7. Missing two or more follow-ups during the Phase (Note: Follow-ups completed out-of-window are not considered "missing")
  - 8. Zero total device uses during the Phase.

The PP Population will be used for a secondary analysis of all efficacy endpoints.

### 7.0 DEMOGRAPHICS AND BASELINE CHARACTERISTICS

Demographics and baseline characteristics will be summarized for the ITT Population. Descriptive statistics will be presented for the continuous variables of age, height, weight, BMI, IRLS total score at baseline, and the duration of RLS symptoms. Frequencies and percentages will be presented for the categorical variables of sex (at birth), ethnicity, race, category of medication that the subject is refractory to, and categories of medication that the subject is currently taking for the indication of RLS, among the following categories: Dopamine agonist, Alpha-2-delta ligand, Opioid, Benzodiazepine, and Other.

### 8.0 EFFICACY AND SAFETY ANALYSES

### 8.1 Primary Efficacy Endpoint Analysis

The primary efficacy endpoint is the response on the Clinical Global Impressions-Improvement (CGI-I) scale at Week 4 of Phase 1 relative to Baseline (study entry) where a "successful" response is defined as a response of "Much Improved" or "Very Much Improved". This endpoint will be summarized by treatment group using frequencies and percentages. The null and alternative hypotheses for this endpoint are as follows:

 $H_0: RR_T \leq RR_S$ 

versus

 $H_1: RR_T > RR_S$ 

where  $RR_T$  and  $RR_S$  are the true responder rates for the NTX100 treatment group and the sham control group, respectively. The null hypothesis will be tested using a one-sided normal approximation test for the comparison of two proportions at the alpha = 0.025 level. If there are any missing data for this endpoint, multiple imputation (MI) methods will be used to impute the missing data.

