16.4. Screening

Potential subjects will be screened for eligibility based on the criteria in Section 7 above. Device calibration (Section 16.5 below) will be part of the screening process, consistent with Exclusion Criterion #18. A potential subject who signs the study consent and is eligible will be assigned a study ID number, will be considered enrolled, and will count towards the study's sample size. Potential subjects who fail Exclusion Criterion #18 and experience an adverse event (AE) during device calibration will be assigned a study ID for the purpose of tracking this AE but will not be randomized to a treatment arm and will not count towards the study's sample size.

16.5. **Device calibration**

During screening, the stimulation intensity of the investigational device will be calibrated separated for each leg (left and right), using the demo calibration kit provided by the sponsor. If the subject does not fail Exclusion Criterion #18 during calibration the subject will be randomized within the EDC system, the calibrated values will be programmed into the investigational device kit that corresponds

CONFIDENTIAL

to the randomization number generated. The calibration process is designed to identify the maximally effective settings that are comfortable for each subject. The sponsor may administer the calibration and/or assist in administering the calibration.

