16.7. Randomization

Following consent and enrollment, authorized site staff will be provided with each subject's assigned study device kit number by the EDC system during the randomization process. The site staff will record the assigned randomization number on both the device kit label and the subject's source documents. The site staff will also record the randomization assignment in the Device Accountability Log. Subjects will be randomized in a 1:1 to either:

- NTX100 programmed to ACTIVE mode
- NTX100 programmed to SHAM mode

Randomization assignments will be stratified by study center with randomly chosen block sizes of 4 or 6. Small but randomly determined block sizes preserve treatment assignment balance within study center while maintaining assignment unpredictability. Any Investigator who is discovered to tamper with randomization will be immediately terminated from the study.

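### Randomization is stratified by site, but no between-arm efficacy test, imputation model or summary table uses site; the tests stay valid but turn conservative if sites differ

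*SAP*

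**What the plan says.** SAP 3.2 sets the allocation: "Randomization assignments will be stratified by study center with randomly chosen block sizes of 4 or 6". Protocol 16.7 gives the reason: "Small but randomly determined block sizes preserve treatment assignment balance within study center while maintaining assignment unpredictability".

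The analysis then drops site. SAP 5.2 states: "There will be no adjustment for covariates in any efficacy or safety analysis, unless there are missing data for the primary efficacy endpoint". That exception leads to the imputation model in SAP 5.3, which uses "treatment group and the following covariates as explanatory variables: IRLS at Days 0 and 14 and PGI-I at Day 14", so site is absent there too. The primary endpoint is "tested using a one-sided normal approximation test for the comparison of two proportions at the alpha = 0.025 level" (SAP 8.1). SAP 8.2 analyses PGI-I response the same way, without imputation, and uses plain two-sample t-tests for IRLS, MOS-II, MOS-I and CGI-I score. Key secondary endpoint 6 is a one-sample test in a single arm.

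On the sites themselves, SAP 5.5 adds only a count: "Four to eight clinical sites within the United States will participate in the study". SAP 5.7 plans no subgroup analyses, no table shell is by site, and site appears only as a column and sort key in the listings.

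Protocol 16.14 has the Investigator complete the CGI-I, after seeing the subject's PGI-I answer and holding a short interview. Subjects rate PGI-I, IRLS and MOS-Sleep themselves.

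**The concern.** Blocking within site balances the arms on site. If site also predicts outcome, the between-site part of the variance cancels out of the arm difference, but an unstratified test still counts it as error. The standard error is then too large, the true error rate falls below 0.025, and power is lost.

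Site could plausibly matter for the primary endpoint, because it is a global judgement by a rater who belongs to one site. With 4 to 8 sites, one unusually lenient or strict rater could shape the pooled result, and no planned table would show it. That gap exists whatever the between-site variance turns out to be.

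IRLS is where power is tightest. It produces the largest sample size (112), it is planned at 85% power, and it stands second among the key secondaries in a fixed sequence. Failing it stops formal testing of endpoints 3 to 6.

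**Working it through.** **1. The plan's own figure.** SAP 3.4: 112 completers with 15% dropout. 112 / 0.85 = 131.76, rounded up to 132. This matches.

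The component sizes (42, 42, 112 and 36) cannot be re-derived, because no rates, differences or SDs are given. At 85% power and one-sided 0.025 they imply:
- IRLS, 56 per arm: d = (1.960 + 1.036) × √(2/56) = 2.996 × 0.1890 = 0.566 SD.
- CGI-I response, 21 per arm: about 64–65% active if sham is 20%, or about 75% if sham is 30%. The sham rates are assumptions.

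**2. IRLS t-test, closed form.** Set the total SD to 1, let the ICC (assumed) be the between-site share of variance, and let w = √(1 − ICC). With arms balanced within site, the true standard error is w × √(2/56), but the planned test uses √(2/56). Here d / √(2/56) = 2.997.
- True one-sided error of the planned test: 1 − Φ(1.960 / w)
- Planned power: Φ((2.997 − 1.960) / w)
- Site-adjusted power: Φ(2.997 / w − 1.960)

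For ICC 0.10, w = 0.9487. Planned power is Φ(1.093) = 86.3%, adjusted power is Φ(1.199) = 88.5%, and the true error is 1 − Φ(2.066) = 0.019.

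| ICC (assumed) | Planned power | Site-adjusted power | Gain (points) | True error, planned test |
|---|---|---|---|---|
| 0 | 85.0% | 85.0% | 0 | 0.025 |
| 0.05 | 85.6% | 86.8% | 1.1 | 0.022 |
| 0.10 | 86.3% | 88.5% | 2.2 | 0.019 |
| 0.20 | 87.7% | 91.8% | 4.1 | 0.014 |

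Gains are taken before rounding. Planned power rises with ICC because d is held fixed relative to the total SD. The closed form ignores the degrees of freedom spent on site and incomplete blocks. Simulation with 112 subjects and blocks of 4 or 6 gave slightly smaller gains: at ICC 0.20, 88.5% against 91.9% with 4 sites and 86.9% against 90.3% with 8 sites, or 3.4 points in each case.

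**3. CGI-I response, simulated.** The planned z-test is compared with a site-stratified Cochran–Mantel–Haenszel (CMH) test, for 4 to 8 sites and site-stratified blocks. Site effects are normal on the logit scale with an assumed SD. Around a 30% sham rate (logit −0.847), SD 0.5 puts the middle 95% of sites at about 14% to 53%, and SD 1.0 at about 6% to 75%.

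*Effect implied by 42 subjects (30% against 75%), 112 evaluable:*
- SD 0: 99.8–99.9% for both tests.
- SD 0.5: 99.6–99.8% planned, 99.7–99.8% CMH.
- SD 1.0: 99.0–99.1% planned, 99.4–99.5% CMH.

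A second simulation with unequal site sizes put the gain at no more than about 0.15 points.

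*Much smaller effect (30% sham, log odds ratio 1.0).* Odds of 0.30/0.70 = 0.429, times 2.718, give 1.165, which is a 54% response.
- 132 subjects, SD 0: about 80% for both.
- 132 subjects, SD 0.5: 76% planned, 78% CMH.
- 132 subjects, SD 1.0: 66–67% planned, 72% CMH.
- 112 subjects, SD 1.0: 57–59% planned, 64–65% CMH.

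Under the null (35% in both arms, 132 subjects, SD 1.0), the planned test's one-sided error was 0.015–0.019.

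**4. Subjects per site.** 112 / 4 = 28 and 112 / 8 = 14, so about 14 or 7 per arm at each site.

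**The case against.** The strongest reply is that nothing is invalid. SAP 5.2 declares the unadjusted analysis in advance, it cannot inflate the false-positive rate through site, and any cost falls on the sponsor's own chance of success. All of that stands. At the effect the sample size implies, the primary test has about 99% power or more either way. A site SD of 1.0 is extreme, and the documents support no particular value. That stands too, although the implied effect comes from an earlier prototype, so a smaller one is possible.

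A reader might also infer that site-specific raters and operators produce all the endpoints. The documents do not support this. Only CGI-I is Investigator-rated, and the Investigator sees the subject's PGI-I answer first, which may limit rater drift. On calibration, Protocol 16.5 says: "The sponsor may administer the calibration and/or assist in administering the calibration". The operator therefore need not belong to the site, and calibration comes before randomization and is the same for both arms.

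Nor are site differences wholly hidden. Listings 2.1 to 2.4 carry a site column. Their shells have no arm column, though, so what is missing is a summary by site and arm.

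Finally, the remedy is not free of difficulty. With 7 to 14 subjects per arm per site, a site-by-treatment test has little power and invites over-reading, and up to seven site terms in a logistic imputation model may meet sparse cells.

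**Conclusion.** The mismatch is real: site is a randomization stratum but is absent from every between-arm efficacy test, from the imputation model and from every table. Two stronger conclusions do not follow. The type I error is not inflated; the planned tests are valid and become conservative as sites diverge. And a material loss of power for the primary endpoint is not shown.

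The size rests on a between-site variance that the documents do not give. If sites do not differ, nothing is lost. The IRLS loss matters most, because that comparison has little slack: 1 to 2 points at ICC 0.05 to 0.10 and about 4 at 0.20. For the primary endpoint, a loss of 2 points (SD 0.5) up to 6 to 7 points (SD 1.0, 112 evaluable) needs an effect near 30% against 54%. At the plan's implied effect it is about half a point at most. The missing site-by-arm summary depends on none of these assumptions. The change is worth making as a low-cost improvement, not as a correction of an invalid analysis.

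**What to change.** Amend the SAP before unblinding:

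- Test CGI-I and PGI-I response with a CMH test stratified by site, and report the Mantel–Haenszel risk difference.
- In SAP 5.3, combine that stratified estimate across imputations. The present step combines each arm's responder rate separately, so it needs rewriting.
- Add site as a fixed effect to the IRLS, MOS-II, MOS-I and CGI-I score comparisons. Endpoint 6 has no second arm and needs no change.
- Add site, after merging small sites, to the imputation model.
- Amend SAP 5.2 to allow these terms, and state the merging rule in SAP 5.5.
- Add one table of CGI-I response by site and arm. Label any site-by-treatment check as descriptive.
- Keep the unstratified tests as sensitivity analyses.

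No new data are needed. The costs are SAP wording, one table, a merging rule fixed in advance, the rewritten combination step, and a check for sparse cells in the imputation model.
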